Each intervention session will be audio-recorded for the evaluation of therapist adherence to the protocol, and a random selection of 25% of all sessions conducted will be reviewed by the study PIs. Given that Zoom group sessions will be video-recorded (in order to obtain the audio recording), all video recordings will be destroyed immediately after each session. Additionally, we will conduct individual interviews with participants at the end of the study to evaluate their perceptions of the program. No identifying information will be transcribed as the purpose of this digital recording is to assess treatment integrity. Once the group session audio recordings are reviewed and adherence is discussed with the study interventionist, the recordings will be destroyed. For the individual interviews, we will transcribe all recordings and destroy the audio after transcription. Prior to destruction, the recordings will be kept in a locked filing cabinet in the laboratory of the PIs. Data obtained during audio-recorded qualitative interviews with patients may

be used in future publications but will not be linked with names or identifying information. The audio file will be downloaded from Zoom (or via audio recorder if conducted in person), saved on a password protected computer in our University office, and transcribed for responses to the questions. No names will be included on the typed files. If any personal information comes up during the interview, the information will be redacted from the transcript. Quotes from the interview may be used in future publications but will not be linked with names or identifying information. All audio recordings will be deleted from the network drive where it will be stored, with assistance from the IT department once they have been de-identified and transcribed, no later than 12 months after they are recorded.

7. **Possible Discomforts and Risks:** The risks for this study are minimal and appropriate safeguards are planned and in place to handle risks in a timely and appropriate manner. One area of risk of this study is loss of privacy. There are two ways that privacy is at risk: (a) through data collected and stored by the study team at UF, and (b) by data collected and stored by Apple through participants' use of the Apple Watch. With regard to study team collected data, we cannot guarantee that data will not be unlawfully obtained. The steps described above in "Confidentiality" section will decrease the chances of this. With regard to data collected by Apple, any data the patients share with Apple is subject to the privacy terms of Apple. Patients will be informed during the consent process that the data they share with Apple is not protected by the University. Further, it is generally unsafe for women who are pregnant to engage in weight loss efforts, and it is an exclusion criterion in our study. As such, participants will be withdrawn from the study if they become pregnant.

Protection against potential risks. Participants will fill out several questionnaires about themselves. While these generally carry no associated risks, it is possible that participants might experience some distress from completing these questionnaires due to the sensitive nature of the items. We will take all necessary steps to minimize discomfort and participants will be free to omit any questions that they do not wish to answer. The procedures and activities included in the EMPOWER intervention involve minimal risk. Participants will be informed that they can discontinue study procedures at any time, and they will not be penalized for doing so. The activity tests for the Back Performance Scale may produce discomfort and participants can stop these procedures at any time. An extensive literature on behavioral weight loss interventions suggests that there is very limited risk, particularly if patients are prescribed a calorie goal of greater than 1,000 kcals/day. Participants will be encouraged to maintain a calorie intake within a safe range of 1,200-1,800 kcals per day. With any program that promotes physical activity, there is a small increased risk of musculoskeletal injury; however, the physical activity-focused portion of this intervention will emphasize finding safe activity and approaching it at a safe pace. The PI is a psychologist and is trained to deal with depression. Any participants whose responses during the group sessions or on the PROMIS Depression Short Form (raw score ≥ 33) indicate severe psychological distress (such as severe depression) will be interviewed by the site PI or other appropriately trained professionals for suicide risk and risk of harm to self and others. Participants will be assisted to the emergency room if danger is imminent or referred to either their physician or a mental health professional if necessary.

8. **Potential Benefits to Participants:** Participation in this research will provide the participant with a first-hand look at research and provide them with the opportunity to participate in a new self-management treatment for chronic musculoskeletal pain and overweight/obesity. Participants who complete the EMPOWER intervention may show improvement in pain and weight management. Ultimately, such knowledge may enhance quality of life and reduce pain in the targeted population, as well as lead to advances in the treatment of pain and excess weight in adults. Given the minimal risks associated with the study procedures, the risks are considered reasonable in relation to the potential benefits.

Importance of the Knowledge to Be Gained. Chronic musculoskeletal pain and overweight/obesity result in significant impairments, as well as tremendous individual and societal burden. The data obtained from the current study has the potential to advance treatment strategies for pain and weight management among middle-aged and older adults and may have broader implications for other medical populations likely to suffer from chronic pain and obesity. Moreover, our findings will enhance the understanding of underlying mechanisms contributing to treatment-related effects in pain impact and weight loss.

Inclusion of Women and Minorities. Given sex-specific prevalence of musculoskeletal pain and obesity,¹⁸⁻⁶¹ both male and female subjects will be recruited with the goal of equal gender distribution. It is planned that adult minorities (45-80 years) will be included in the study sample in proportion to census levels in the Gainesville, Florida (Alachua County) community including: 69.9% White, 20.6% Black/African-American, 6.3% Asian, 10.3% Hispanic or Latino, and 2.9% More than One Race. To ensure that the study sample includes census levels of minorities, we will assess their representation periodically over the course of the study and adjust recruitment or over-sample as needed.

9. **Conflict of Interest:** There is no conflict of interest involved with this study beyond the professional benefit from academic publication or presentation of the results.

References

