Cover Page for ClinicalTrials.gov

Document:

Protocol

Official Study Title:

Empowering the Management of Pain-Obesity-Weight through Enhanced Reward

NCT Number:

NCT04851587

Document Date:

07/11/2022

Protocol

- 1. Project/Grant Title:** Empowering the Management of Pain-Obesity-Weight through Enhanced Reward (EMPOWER)
- 2. Investigators:** [name]. (PI)
[name]. (PI)
[name]. (Co-I)
[name]. (Co-I)
[name]. (Co-I)
- 3. Abstract:** Chronic low back pain (cLBP) is the leading cause of disability worldwide and is one of the top reasons for seeking healthcare. High-impact low back pain is particularly problematic, defined as chronic pain accompanied by significant restrictions in work, social, and/or self-care activities for six months or more. High-impact pain is associated with greater pain-related disability, opioid use, and healthcare costs compared to pain of lower impact. Thus, efforts to reduce chronic pain impact have become a public health initiative. Low back pain and overweight/obesity are highly comorbid; overweight and obese individuals are up to 43% more likely to have cLBP compared to normal weight individuals. Together, the additive effects of overweight/obesity and chronic pain may play a larger role in increasing the risk for other adverse health-related comorbidities. Therefore, the aim of this exploratory study is to examine the feasibility and acceptability of an integrated pain and weight management intervention (EMPOWER) for middle-aged and older adults with moderate-to-high impact low back, knee, and/or hip pain by addressing mechanisms of environmental reward and positive affect. Forty adults (ages 45-80 years) with comorbid overweight/obesity ($BMI \geq 25 \text{ kg/m}^2$) and moderate-to-high impact cLBP will be assigned to an 8-month intervention, whereby they will receive a group- and telephone-based program featuring integrated behavioral weight loss treatment and cognitive-behavioral pain coping therapy, including systematic pleasant activity scheduling and values-clarification techniques. Assessments will be conducted at baseline and at the 4- and 8-month time points. The proposed research will be a step toward the development of therapeutic modalities aimed at improving pain and weight management in adults with comorbid cLBP and overweight/obesity, and will provide essential information to guide a larger, randomized-controlled trial of the EMPOWER intervention.

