Other recruitment. Participants will also be recruited from clinic and community flyers, newspaper advertisement, UF HealthStreet, and the UF Pain Research and Intervention Center of Excellence (PRICE), Institute on Aging Pepper Center, and the University of Florida Jacksonville Aging Studies Center Research Participant Recruitment registries.

Screening. All potential participants will undergo an initial phone screening interview, via telephone or in person. We have requested a waiver of written informed consent to retain this information; we will provide verbal consent information and allow participants the chance to ask questions. The initial screening will include questions regarding pain, age, weight, and additional health history information to ensure that no exclusion criteria are present. For participants not affiliated with the University of Florida Health Care system, we will be asking a series of questions to assess any instability of the spine. If instability is determined, the participant must contact their own physician for written permission to partake in the study. If still eligible, participants will be scheduled for an individual in-person baseline assessment during which informed consent will be reviewed, medical and demographic history will be obtained to ensure eligibility, questionnaires will be administered, and a physical performance battery will be conducted to examine lower extremity function. At the completion of the baseline assessment, eligible participants will be scheduled for the intervention program (90 min/session).

Participants. A total of 40 middle-aged and older adults with moderate-to-high impact chronic musculoskeletal pain (e.g., lower back, knee, hip) and overweight/obesity ($BMI \geq 25 \text{ kg/m}^2$) will be targeted. Assuming a 20% attrition rate, an additional 8 subjects will be enrolled, leaving a total of 48 participants to be recruited for study intervention procedures (we anticipate recruiting a total of 60 people to account for screen failures). Participants will still be included if they report the presence of medical pain comorbidities; however, subjects must identify musculoskeletal pain as their primary pain condition.

Inclusion Criteria

- 45-80 years of age
- Have a $BMI \geq 25 \text{ kg/m}^2$
- Endorse pain in the lower back region (i.e., space between the lower posterior margin of the rib cage and the horizontal gluteal fold), knees, or hips

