Specific Aim 1: Evaluate the acceptability of the EMPOWER intervention, as indicated by treatment engagement and participant reported treatment credibility and satisfaction, and potential for treatment efficacy. We will examine treatment engagement at each session and will measure

Table 2. Study Measures

Variable	Measure	Time-Point (Month)		
		0	4	8
Participant Engagement	Treatment Engagement Ques.	Every session		
Treatment Credibility	Credibility/Expectancy Scale	X		
Treatment Satisfaction	CSQ-8		X	X
Qualitative Evaluation	Qualitative Interview			X
Pain Impact	RTF Impact Stratification	X	X	X
Body Weight	By Digital Scale	X	X	X
Intensity, Interference, Phys. Function	PROMIS Pain Measures	X	X	X
Functional Performance	BPS	X		X
Back-Related Disability	RMDQ	X	X	X
Physical Activity	IPAQ	X	X	X
Pleasant Activity Engagement	Self-Reported Engagement	X	X	X
Reward from Activities	MAPA	X	X	X
Positive Affect	PANAS	X	X	X
EMA of Pain Intensity	Smartwatch Ratings	X		X
EMA of Mood and Physical Activity	Smartwatch Ratings	X		X
Quality of Life	WHOQol Bref	X	X	X

Note: Ques=Questionnaire; Phys=Physical. See text for a full description of abbreviations for study questionnaires.

several aspects of global acceptability at baseline and at the 4- (mid-intervention) and 8-month (end of intervention) assessment period.

Session-level Engagement. Treatment engagement will assess participants' effort exerted during group activities/phone calls (using a 9-point Likert rating scale), completion of homework (yes/no), and engagement in group and individual discussions (using a 9-point Likert rating scale). Responses will be examined after sessions and after all four cohorts are complete (considering the mean and range of Likert ratings for each questionnaire item). We will also develop a 95% CI around the Likert ratings and examine if our metric for success falls within that interval (i.e., ≥ 6 on a 9-point Likert scale).

Global Treatment Engagement. The mean portion of group and phone sessions attended will be examined across the entire sample, as well as trends in the portion of sessions attended across the four cohorts. We will determine if our metric for success falls within a 95% CI around our identified threshold for success. The percentage of participants who complete $\geq 80\%$ of group and phone sessions combined will also be measured, as well as the portion who complete $\geq 70\%$ of group sessions and $\geq 70\%$ of phone sessions (considered separately).

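### The 20% attrition allowance is taken from the target of 40, not from those enrolled, so 48 leave about 38; the abstract also says 40, not 48, are assigned

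*Combined protocol and SAP*

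**What the plan says.** Section 6 (Research Plan), under Participants, sets the target: "A total of 40 middle-aged and older adults with moderate-to-high impact chronic musculoskeletal pain", with overweight or obesity. It then adds the allowance for loss: "Assuming a 20% attrition rate, an additional 8 subjects will be enrolled, leaving a total of 48 participants". The 48 are described as "48 participants to be recruited for study intervention procedures", and the same sentence goes on to say "we anticipate recruiting a total of 60 people to account for screen failures".

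The abstract (section 3) gives another count. It says that forty adults "will be assigned to an 8-month intervention", and it mentions neither 48 nor an attrition allowance.

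Two parts of Statistical Methods bear on this. Under Specific Aim 2, the retention metric is at least 80% completing the 8-month assessment, counted among those who enroll, in the final two cohorts. Under Specific Aim 1, engagement is summarised over everyone: "The mean portion of group and phone sessions attended will be examined across the entire sample".

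**The concern.** There are two separate points.

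First, an attrition rate is normally a fraction of the people who start, and that is the denominator the protocol's own retention metric uses. Here the 20% was applied to the number wanted at the end. The number added is then too small for the stated rate, and the planned enrolment does not deliver the target under the plan's own assumption.

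Second, the abstract and section 6 give different numbers, 40 and 48, for the group going into the intervention.

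The stakes are limited, but they touch an aim of the study. Specific Aim 2 is about meeting recruitment and retention metrics, so the planned intake should be one figure and the number expected to remain should follow from it. As written, a retention of exactly 80% across all 48 would still fall short of 40.

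**Working it through.** **Inputs.** Target 40, attrition 20%, addition 8, total 48, and 60 recruited to cover screen failures (all section 6, Participants); forty assigned (section 3, Abstract).

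**The plan's own figure.**
- 0.20 × 40 = 8, and 40 + 8 = 48.
- So the stated 48 is reproduced exactly by N = n × (1 + d), with n = 40 and d = 0.20.

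**What 48 enrolled would leave.** Expected number remaining = N × (1 − d).
- 48 × 0.80 = 38.4.
- Shortfall: 40 − 38.4 = 1.6.
- Attrition that 8 extra subjects cover: 8/48 = 16.7%.
- Retention needed to keep 40: 40/48 = 83.3%.

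**What the stated rate would require.** N = n / (1 − d) = 40/0.80 = 50, that is, 10 extra rather than 8. Check: 50 × 0.80 = 40.

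**Chance of keeping at least 40.** The number remaining is taken as binomial with probability 0.80, which assumes that losses are independent between participants.

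| Enrolled | Expected to remain | P(at least 40 remain) |
|---|---|---|
| 48 | 38.4 | 0.358 |
| 50 | 40.0 | 0.584 |

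The second row is the proper comparison. Even a correctly inflated sample reaches 40 only a little more often than not, because 40 is then just the expected value.

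**Effect on precision.** Half-width of a 95% confidence interval for a mean, in SD units = t(0.975, n − 1)/√n.
- n = 40: 0.320
- n = 38: 0.329
- Difference: 0.009 SD

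**Abstract against section 6.**
- 48 − 40 = 8 participants.
- Read literally, with the same 20% attrition, the abstract's forty would leave 40 × 0.80 = 32.

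**Screen failures.** The 60 is not affected. It allows for 60 − 48 = 12 screen failures, and 12/60 = 20% of those recruited.

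**The case against.** **The size is close to nil.** The expected gap is 1.6 people, the conventional enrolment differs from 48 by two, and no success metric uses 40. This stands, and it sets the severity. It does not make the statement correct.

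**There is another reading of the 8.** The paragraph could describe a replacement plan: enroll 40, expect to lose 8 of them, enroll 8 more. The 8 is then 20% of its stated base, and the paragraph does not define the attrition denominator. But this reading still aims at 40 remaining, and it ignores loss among the replacements: 8 × 0.20 = 1.6, the same shortfall.

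**The probability of 0.36 looks worse than it is.** This is fair. The contrast that matters is 0.36 against 0.58. Participants treated in groups may also not drop out independently, so both figures are only indicative.

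**Assigned and recruited are different words.** The protocol separates enrolling from commencing treatment, with a metric of at least 90% commencing, and an abstract may simply repeat a headline target. The abstract's forty may well be the retained target loosely worded. Even so, the distinction does not turn 48 into 40: 90% of 48 is 43.2. As written, forty is the number assigned, and the two places need to agree.

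**Conclusion.** Both points hold, and both are minor.

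On the first, the stated sample size does not deliver its own target at its own attrition rate: about 38 would be expected to remain, not 40. This rests on taking 40 as the number wanted after attrition. The paragraph does not say so outright, but there would be little reason to add subjects for attrition otherwise.

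On the second, the difference of 8 between the abstract and section 6 needs no assumption about attrition.

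No conclusion of the trial turns on either. Only measures taken after the loss are affected, and those by about 0.01 SD in half-width. Summaries over all who enroll, such as session attendance, do not depend on whether 38 or 40 remain.

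**What to change.** In section 6, Participants, replace the sentence that targets 40 and the attrition sentence with a statement that 48 will be enrolled in the intervention and that, at 20% attrition, about 38 are expected to remain. Keep the population description and the 60 for screen failures. In the abstract, change forty to 48 adults assigned to the intervention. While editing, the sponsor could also name the assessment (4 or 8 months) to which the 20% refers, since the paragraph does not say.

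The cost is two sentences in section 6 and one in the abstract, with no change to enrolment, procedures or analysis. What the sponsor gives up is 40 as the stated target.

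If the sponsor prefers to keep 40 as the number expected to remain, the arithmetic requires 50 enrolled. That costs two more participants, and at the screen-failure share implied by 48 of 60 it means about 63 recruited (50/0.80 = 62.5). Given the small gain in precision, restating the numbers is enough.

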participation as this could interfere with completion of the study intervention. The alternative/equivalent version of the MoCA (Version 7.2) will be used to decrease possible learning effects when the MoCA (Version 7.1) has been administered within the past 3 months of study participation. This will serve as a safeguard for test-retest effects for participants who may have recently participated in studies requiring the administration of this instrument.

Measures of Treatment Acceptability. We will obtain acceptability data at each session and at study assessment points. After each group/phone session, the study interventionist and participants will complete treatment engagement questions adapted for the current study to assess participants' effort exerted during group activities/phone calls, completion of homework, and engagement in discussions. They will also answer open-ended questions on their satisfaction with and usefulness of the session components. At the baseline assessment, participants will complete an adapted measure of treatment credibility and expectancy⁵ to assess the perceived credibility of treatment and expectation for improvement. At 4 and 8 months (if applicable), the 8-item Client Satisfaction Questionnaire (CSQ-8)² will be administered to measure general treatment satisfaction, perceived quality of treatment, and willingness to recommend the treatment. Additionally, at 4 and 8 months (if applicable), participants will complete Likert ratings and answer open-ended questions on their satisfaction with the intervention components (e.g., values clarification exercises) and recommendations for intervention improvement. Responses to all acceptability measures will be used to refine the protocol across cohorts.

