Qualitative Interviews: To obtain more in-depth perspectives, study PIs will conduct qualitative interviews with a portion of participants who have completed the intervention. Interviews will either occur in person or on HIPAA-compliant Zoom with only audio activated (no video). From our total sample we will purposefully sample for participants who achieved a reduction in pain impact and weight and from those who did not see a reduction in pain impact and/or weight. We will interview a minimum of 12 participants but will continue interviews if we do not reach thematic saturation. The structured interview will include questions about participant perceptions of the intervention modality and structure, group and individual session content, and barriers to engagement in pleasant activities. These will be conducted around the Month 4 timepoint if participants complete only the 8 core intervention sessions, and will occur around the Month 8 timepoint if all 16 intervention sessions are completed. Directed content analysis will be used to analyze the data.²⁸

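### The acceptability interviews cover only participants who completed the intervention, so nobody who stops before finishing the core sessions is asked why

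*Combined protocol and SAP*

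**What the plan says.** The main description is in section 6 of the protocol, under Qualitative Interviews: "study PIs will conduct qualitative interviews with a portion of participants who have completed the intervention". The timing rule follows the same idea. "These will be conducted around the Month 4 timepoint if participants complete only the 8 core intervention sessions"; those who complete all 16 sessions are interviewed around Month 8.

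Selection within that frame is purposive and by outcome. "From our total sample we will purposefully sample for participants who achieved a reduction in pain impact and weight", and also for "those who did not see a reduction in pain impact and/or weight". On numbers: "We will interview a minimum of 12 participants but will continue interviews if we do not reach thematic saturation". The interview covers views of the modality and structure, of session content, and of what gets in the way of pleasant activities.

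Two other places bear on the point:

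- The Confidentiality section describes end-of-study interviews with participants and gives no restriction to completers.
- Measures of Treatment Acceptability states how the information will be used: "Responses to all acceptability measures will be used to refine the protocol across cohorts".

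**The concern.** Acceptability is Specific Aim 1, and the plan means to learn from it between cohorts. It also allows retention strategies to be adjusted during the pilot, and it judges retention on the final two cohorts. For both purposes the most useful informants include people who began the programme and stopped. The interview is the one place where they could be asked about it in depth, and the stated frame leaves them out.

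The split by outcome does not bring them back. It needs change in pain impact and weight, which may be missing for someone who stopped and did not return for assessment. The larger trial could then be designed with good information on what completers liked and disliked, and little on why others left.

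**Working it through.** **1. Who has an interview slot.** Reading the frame and the timing rule together:

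- finishes the 8 core sessions only: interviewed around Month 4;
- finishes all 16 sessions: interviewed around Month 8;
- stops before finishing the core: no slot.

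Declining the optional sessions therefore excludes nobody. Stopping during the core does.

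**2. Whether another measure fills the gap.**

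- Session ratings and open-ended session feedback come only from sessions attended. They concern that session's components and end when the person stops.
- Attendance (Global Treatment Engagement) is taken over all participants. It shows that people stopped, not why.
- Credibility is measured at baseline, before anyone can stop.
- The CSQ-8 and the open-ended programme questions are given at 4 and 8 months where applicable. They reach a stopper only if that person still attends the assessment. No administration at withdrawal is described.
- Recruitment reporting includes reasons for ineligibility. Retention reporting gives only the proportion attending assessments.

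None of these asks about reasons for stopping.

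**3. The plan's own figure.** Under Participants: "Assuming a 20% attrition rate, an additional 8 subjects will be enrolled, leaving a total of 48 participants". With the target of 40, 40 × 0.20 = 8 and 40 + 8 = 48, so the figure is reproduced. Applying 20% to those enrolled gives 48 × 0.20 = 9.6, or about 10. The number of stoppers is thus 8 by the plan's allowance or about 10 by its rate, assuming that attrition means stopping the intervention.

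**4. What an unrestricted draw would give.** For 12 interviews drawn at random from 48 participants, D of whom stopped, the expected number of stoppers is 12 × D/48, and the chance of none is C(48 − D, 12)/C(48, 12).

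- D = 8: expected 12 × 8/48 = 2.0; chance of none 0.08.
- D = 10: expected 12 × 10/48 = 2.5; chance of none 0.04.

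Under the stated frame the number is 0 by rule.

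**5. How far the picture could shift (illustration only).** Let c be the share of completers with a negative view, s the share of stoppers, and d the proportion stopping. The share over everyone is (1 − d)c + ds. The documents give no values, so assume c = 10% and s between 50% and 80%.

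- d = 10%: 14% to 17%.
- d = 20%: 0.8 × 10% + 0.2 × 50% = 18%, up to 0.8 × 10% + 0.2 × 80% = 24%.
- d = 30%: 22% to 31%.

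Completers alone would show 10%. If stoppers hold the same views as completers (s = c), the shift is zero.

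**6. Effect on the Aim 1 criteria.** The criteria under Statistical Methods use session ratings, attendance, the CSQ-8, credibility and outcome changes. No criterion uses the interviews, so the frame changes none of the numeric results.

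**The case against.** A reader might infer that Aim 1 as a whole is biased upward. The documents do not support that. The interviews are a supplement with no success threshold, and they do not enter the confidence-interval rule for progression. Stopping lowers the attendance measure, because attendance is taken over all participants. Credibility is collected before anyone can stop. People who did not improve are sampled on purpose, which works against a one-sided set of interviews. Early stoppers also leave open-ended comments on the sessions they attended. All of this stands.

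A reader might also assume that people stop because they find the programme unacceptable, or that the interview's item on barriers concerns attendance. The plan does not say why people will stop, and the item concerns pleasant activities, which completers can answer well.

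The size can be questioned too. The 20% is not defined as stopping the intervention, and retention is measured by attendance at assessments. Random sampling is only a yardstick for interviews chosen purposively and continued to saturation. These objections limit the size and leave the direction open. They do not supply the missing reasons for stopping.

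Finally, the reference to the total sample and the Confidentiality text could be read as admitting stoppers. Both are looser than the explicit completer restriction, and the timing rule offers stoppers no slot. They are grounds for reconciling the text and do not close the gap.

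**Conclusion.** The point holds in a limited form. As written, the interviews exclude anyone who stops before finishing the 8 core sessions, and no other listed measure asks why they stopped. The in-depth acceptability evidence will lack that information and may lean favourable. A favourable lean is plausible but not demonstrated, and it does not reach the numeric Aim 1 criteria.

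If attrition means stopping the intervention, about 8 to 10 of 48 participants are outside the frame, and 2.0 to 2.5 expected interviews with such people become none. The percentages in step 5 rest on assumed views and show only the possible scale. The change is worth making because acceptability is the central question and the remedy is small.

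**What to change.** - Open the interview frame to everyone who attended at least one session.
- Purposively include some participants who stopped before finishing the core, for example 2 to 3. This number is a judgement guided by the 2.0 to 2.5 above. Select them on completion status, since their outcome change may be unknown, and offer the audio-only Zoom route that the plan already allows.
- Add a question on reasons for stopping, and state when stoppers will be interviewed.
- Report findings by completion status, noting that so few interviews with stoppers are unlikely to reach saturation by themselves.
- Reconcile the Qualitative Interviews text (completers versus total sample) with the Confidentiality section. At the same time, align the interview timing with Table 2, which shows Month 8 only.

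The cost is modest. Early stoppers are harder to reach and some will decline. Within the minimum of 12, 2 to 3 such interviews leave 9 to 10 for completers; otherwise a few interviews are added beyond 12.
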